3 DATA ANALYSIS CONSIDERATIONS

3.1 General presentation of summaries and analyses

Statistical analysis and generation of tables, figures, subject data listings, and statistical output will be performed using SAS® Version 9.3 or higher unless otherwise specified. All tables and listings will use Courier New font size 9.

Descriptive statistics will be displayed to provide an overview of the study results.

For categorical parameters, the number and percentage of subjects in each category will be presented. Unless otherwise noted, the denominator for percentages will be based on the number of subjects included in the respective analysis set. Subjects with missing data can generally be accounted for using one of the 2 following approaches:

- Percentages will be summarized based on all subjects in the analysis set and a “Missing” category (corresponding to subjects with missing data for the variable being summarized) will be included as the last row in the list of categories being summarized (this approach will be used when reporting demographics and Baseline characteristics, some ADA_b and NAb tables and some shift tables from Baseline for laboratory data).
- Percentages will be based only on those subjects with observed data for the variable being summarized. As the denominator may be different from the number of subjects in the analysis set being considered, the denominator should be displayed in the table. The general format for displaying this will be “n/Nsub (%)”.

Unless otherwise noted, all percentages will be displayed to one decimal place. No percentage will be displayed for zero counts, and no decimal will be presented when the percentage is 100%.

Unless stated otherwise, continuous endpoints will be expressed as a change from Baseline which will be calculated as the value at a specific timepoint minus the value at Baseline.

For continuous parameters, descriptive statistics will include number of subjects with available measurements (n), arithmetic mean, standard deviation (SD), median, minimum, and maximum (unless otherwise stated).

For hs-CRP variable, the summary statistics should contain arithmetic mean, geometric mean, geometric coefficient of variation (CV), median, first and third quartile (Q1 and Q3), minimum and maximum (for the value and ratio to Baseline). The geometric CV (%) will be calculated using the following formula:

$$CV = \sqrt{e^{SD_{ln}^2} - 1}$$

where SD_{ln} represents the standard deviation of the ln-transformed hs-CRP values.

For BKZ PK concentrations, geometric mean, geometric CV, 95% confidence intervals (CIs) for geometric mean (assuming log-normally distributed data) will be calculated if at least $\frac{2}{3}$ of the values of interest are above the lower limit of quantification (LLOQ). If this is not the case, only median, minimum and maximum will be presented.

Decimal places for descriptive statistics will always apply the following rules:

- “n” will be an integer.
- Mean, SD, SE, and median (Q1 and Q3 where applicable) will use 1 additional decimal place compared to the original data (for a derived score, number of decimals of the original data considered is the one obtained where deriving the score in the absence of missing data).
- Coefficient of variance (CV [%]) will be presented with 1 decimal place.
- Minimum and maximum will have the same number of decimal places as the original raw value.

If the number of decimal places reported in the original data is varied then either the maximum raw number of reported decimal places or 3 will be used, whichever is the lowest, as a guide for the descriptive statistics.

Table 7–1: List of decimals for continuous efficacy endpoints

Continuous efficacy endpoint	Decimal place used for minimum and maximum	Decimal places used for Mean, SD (or SE) and median
BASDAI	1	2
DAPSA	1	2
DAS28[CRP]	2	3
EQ-5D-3L dimension scores	0	1
EQ-5D-3L (VAS)	0	1
FACIT-Fatigue subscale score	1	2
HAQ-DI	3	4
hs-CRP	2	3
LDI	1	2
LEI	1	2
mNAPSI	0	1
PASDAS	1	2
PASI	1	2
PGA-Arthritis / PhGA-Arthritis	0	1
PGA-PsA / PhGA-PsA	0	1
PsAID-12	1	2
PsAQoL	1	2
PsARC	1	2
PtAAP	0	1
SF-36	2	3
SPARCC	1	2

TJC / SJC	1	2
WPAI-SHP	1	2

BASDAI=Bath Ankylosing Spondylitis Disease Activity Index; DAPSA=disease activity index for psoriatic arthritis; DAS28[CRP]=disease activity score-28 based on C-reactive protein; EQ-5D-3L=Euro-Quality of Life 5-Dimensions 3 Level version; FACIT=Functional Assessment of Chronic Illness Therapy; HAQ-DI=Health Assessment Questionnaire – Disability Index; hs-CRP=High sensitivity C-reactive protein; LDI=Leeds Dactylitis Index; LEI=Leeds Enthesitis Index; mNAPSI=Modified Nail Psoriasis Severity Index; PASDAS= Psoriatic Arthritis Disease Activity Score; PASI=Psoriasis Area and Severity Index; PGA-Arthritis=Patient’s Global Assessment of Arthritis; PGA-PsA=Patient’s Global Assessment of Psoriatic Arthritis; PhGA-Arthritis=Physician’s Global Assessment of Arthritis; PhGA-PsA=Physician’s Global Assessment of Psoriatic Arthritis; PHQ-9=Patient Health Questionnaire-9; PSAID-12=Psoriatic Arthritis impact of disease-12; PsAQoL=Psoriatic Arthritis Quality of Life; PsARC= Psoriatic Arthritis Response Criteria; PtAAP=Patient’s assessment of Arthritis Pain; SF-36=Short-Form 36-item Health Survey; SJC= Swollen Joint Count; SPARCC= Spondyloarthritis Research Consortium of Canada ; TJC=Tender Joint Count; WPAI-SHP=Work Productivity and Activity Impairment questionnaire – Specific Health Problem

Unless stated otherwise, statistical tests of efficacy variables will be performed 2-sided and p-values will be rounded to 3 decimal places. P-values less than 0.001 will be presented as “<0.001” and p-values greater than 0.999 will be presented as “>0.999.” Statistical comparison will be performed at the 0.05 level of significance. Least square means (LSM), odds-ratios (OR) and corresponding confidence intervals (CI) will be presented using 3 decimals.

UCB uses SAS in a 64-bit Windows environment, and it is well-documented that in this environment the maximum accuracy of any numeric value is 15 significant digits. However, SAS by default does not limit the accuracy of numeric values to 15 significant digits which, in certain instances, may result in inaccurate representation of the data and cause errors when used in subsequent calculations, particularly when comparing a value to a chosen threshold. This, in turn, could potentially result in a change in classification of a subject from a responder to a nonresponder (and vice versa) if these values occur on a threshold used in the evaluation of response (or a critical laboratory value for example).

Therefore, in order to avoid issues caused by inaccurate floating point representation of numeric values, temporary variables are created (ie, for absolute values, change and percentage change from Baseline) during programming which are rounded to 12 decimal places prior to comparison to a specific threshold in the derivation of a response parameter. This does not imply inherent rounding on the analysis variables for absolute value, change or percentage of change which are retained unrounded in the final analysis dataset. Thus, rounding is applied exclusively during the derivation of new response parameters or critical value variables, and the rounded values are created on a temporary basis only.

The SAS® outputs supportive of any inferential statistics that are part of the hierarchical testing procedure (ie, all inferential statistics associated with the endpoints in [Table 7–4](#) will be provided as a separate PDF document in addition to TFLs. These outputs will be included in the ‘Documentation of Statistical Methods’ section of the clinical study report.

The order of treatment groups to be presented in tables from left to right will be:

- Placebo
- Bimekizumab 160mg Q4W

Selected tables may also include columns for all subjects (regardless of study treatment).

The abbreviation for bimekizumab is BKZ and will be used in tables and listings headers. In the TLFs subjects randomized to bimekizumab 160mg will be labeled as “BKZ 160mg Q4W”.

Per protocol, visit windows of ± 3 days from the first dose at all visits through Week 16 are permissible. For the SFU Visit, the visit should occur no more than 3 days prior to the scheduled visit date and within 7 days after the scheduled visit date. Only data collected at the scheduled visit will be included in the analysis. The only deviation may concern unscheduled vendor data as explained in [Section 10.5](#).

All by-visit summaries will contain nominal (ie, scheduled) visits only. Unscheduled visits will not be mapped to scheduled visits except for some assessments that may occur within 3-day time window of a scheduled visit. In that case, the assessment will be mapped to the corresponding scheduled visit and will be used for the analysis unless the data are present for that scheduled visit.

Assessments collected at unscheduled visits will only be listed, except in the case of determining treatment-emergent markedly abnormal criteria for laboratory and vital sign parameters where all post-Baseline (scheduled and unscheduled) values will be summarized. For PK, immunological and immunogenicity analyses, SFU data will be a part of the data reported in some tables ([Section 9](#)).

For by-visit tables summarizing efficacy data, the SFU visit will not be included, but SFU efficacy data will be listed. By-visit tables summarizing safety will however include the SFU visit.

A complete set of data listings containing all documented data and all derived data (eg, change from Baseline) will be generated.

Repeated visits will not be summarized but listed.

Unless otherwise stated, listings will be sorted by treatment, subject number within each treatment group (not randomization number), variable (if applicable) and visit (if applicable, including timing relative to dosing if applicable). For listings including nonrandomized subjects, the nonrandomized subjects will be shown first in the listing, ordered by subject number. All listings will include repeat and unscheduled measurements; such measurements will appear in chronological order together with the scheduled visits, ie, a repeated measurement will appear directly after the visit and time relative to dosing for which the repeat measurement was performed. In all the listings dates will be presented in the format 'YYYY-MM-DD' and times will be presented in 24h clock format as 'hh:mm'.

3.2 General study level definitions

3.2.1 Relative day

The relative day will be included in some listings. The way that relative day is calculated depends on when the given event occurs relative to the date of first study drug administration.

- If the event starts (stops) on or after the first dose of study drug administration, but prior to the study drug stop date, relative day is calculated as start (stop) date of the event minus first dose date of study drug dose + 1.

Relative day 1 is the date of first study drug administration.

- If the event starts (stops) after the last dose of study drug administration, the relative day is calculated as start (stop) date of the event minus most recent study drug dose date. The relative day in this situation should be preceded by a '+'

- If the event starts (stops) before the first dose of study drug administration, the relative day is calculated as start (stop) date of the event minus first dose date of study drug dose. The relative day in this situation should be preceded by a '-'.
Relative day will only be computed for fully completed dates and will be left blank for partial dates.

Relative day will only be computed for fully completed dates and will be left blank for partial dates.

For AEs, relative days for start and stop dates will be calculated as the number of days since the first injection of the medication. For non-treatment emergent AEs, relative day of onset will be negative if the event started before the date of first dose. A complete date must be established in order to correctly identify the AEs. [Section 4.2.3](#) describes imputation rules in case of missing data for AEs.

3.2.2 Mapping of assessments performed at Early Termination Visit

If the early termination visit occurs at a scheduled visit as outlined in the schedule of assessments, then no mapping is necessary, and any early withdrawal assessments should correspond to that scheduled visit. Early termination visit assessments that do not have a scheduled visit with a matching date will be assigned a visit based on the protocol defined visit windows (± 3 days from first dose to Week 16, and -3 to +7 days from the final dose for the SFU Visit). For early discontinuation visits that fall between protocol defined visit windows and not within them, the later of the 2 visits will be assigned.

If there is an existing scheduled site visit in the window, then the assessments at the ET visit will be mapped to the next scheduled site visit.

The ADAb assessments and PK are exceptions to this rule:

- ADAb levels, PK from an ET visit will be mapped to the next visit where antibody levels / PK are measured.

3.3 Definition of Baseline values

A Baseline value for a subject is defined as the latest measurement for that subject up to and including the day of administration of first study medication (ie, generally Visit 2 by default), unless otherwise stated.

By default, for randomized subjects for which no start date of treatment is available, the Baseline value will be considered as the last available value prior to the randomization date.

If a Baseline assessment is taken on the same day as first administration of study medication, it is eligible to be used as the Baseline value, even in the case that the time of the assessment is recorded as taking place after the time of first study medication administration. This is considered acceptable as this measurement is still the best representation of the Baseline value of the given assessment since it is highly unlikely that the study medication could have an impact on any measurement in such a short period of time. However, such cases should be rare as study center personnel are instructed to do all assessments at the Baseline visit prior to administering study medication. One exception to this rule is plasma concentration. If Baseline plasma concentration is measured at a time after the first administration of study medication, then it should not be eligible to be considered as a Baseline plasma concentration. Such cases should be discussed with the quantitative clinical pharmacologist.

If a Baseline measurement is missing or not collected, and a Screening value is available, the Screening value will be utilized as Baseline instead. If no measurement is available prior to receiving study medication, then the Baseline value is treated as missing.

Baseline values for component scores should be computed using components from the same visit where the relevant measurements were recorded prior to dosing. For example, if the Screening Visit has all of the components, and the Baseline visit is missing one or more components, the Baseline value for the component score should be calculated using the Screening Visit values.

When the time of first dose is derived, it should be based on the first injection of study treatment, regardless of whether or not it is an active treatment.

Chest x-ray performed within 3 months before the Screening Visit is considered as Baseline measurement.

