10.4 Vital signs, physical findings, and other observations related to safety

10.4.1 Vital signs, weight and physical findings

The following results will be tabulated for all vital sign variables (systolic blood pressure (mmHg), diastolic blood pressure (mmHg), and pulse rate (beats/min), by treatment group and visit:

- A summary of the absolute and change from Baseline value

- A summary of the number and percentage of subjects experiencing at least one markedly abnormal value for a vital sign variable as defined in [Table 10–6](#).

Table 10–6: Definitions of markedly abnormal blood pressure values

Parameter (unit)	Markedly abnormal low	Markedly abnormal high
Systolic blood pressure (mmHg)	<90 and a decrease from Baseline of ≥ 20	>180 and an increase from Baseline of ≥ 20
Diastolic blood pressure (mmHg)	<50 and a decrease from Baseline of ≥ 15	>105 and an increase from Baseline of ≥ 15

For the Baseline visit where several BP assessments are taken, the individual observed data assessments as well as the mean of these assessments will be summarized and listed (pre-dose, 30 min post-dose and 1-hour post-dose).

Treatment-emergent markedly abnormal values will be analyzed on the SS.

Vital signs measurements will also be listed by visit and timing relative to dosing including changes from Baseline. The listing will also include details of abnormal value based on flags as defined in [Table 10–6](#) (“L” for markedly abnormal low and “H” for markedly abnormal high).

Similarly, physical examination findings together with the details of abnormalities (when applicable) will be listed by treatment group, subject and visit.

Body weight will also be listed.

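### Read literally, the Baseline rule in SAP Section 3.3 makes the planned 1-hour post-dose Day 1 blood pressure the Baseline, and Section 10.4.1 does not override it

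*SAP*

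**What the plan says.** Section 3.3 of the SAP sets the general rule. Baseline is the "latest measurement for that subject up to and including the day of administration of first study medication", which cuts by day and not by time. The rule applies "unless otherwise stated". A value taken on the day of first dose qualifies "even in the case that the time of the assessment is recorded as taking place after the time of first study medication administration". The reasons given are that an effect so soon after dosing is very unlikely, and that "such cases should be rare as study center personnel are instructed to do all assessments at the Baseline visit prior to administering study medication". One carve-out follows: "One exception to this rule is plasma concentration". Vital signs are not exempted. Later in the section comes the sentence "If no measurement is available prior to receiving study medication, then the Baseline value is treated as missing".

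Section 10.4.1 covers vital signs. For the Baseline visit it says that several blood pressure readings are taken, and that the individual values and their mean "will be summarized and listed (pre-dose, 30 min post-dose and 1-hour post-dose". It does not name any of these, or the mean, as the Baseline for change from Baseline or for Table 10-6. That table calls a systolic value markedly low if it is below 90 mmHg and has fallen by at least 20 mmHg from Baseline. It has matching rules for diastolic pressure and for high values. Section 3.1 says that the markedly abnormal summary for vital signs uses post-Baseline values, scheduled and unscheduled.

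**The concern.** The allowance for post-dose values in Section 3.3 is meant for the odd assessment done out of order. For blood pressure, two of the three Day 1 readings are post-dose by design. The premise that such readings are rare is therefore contradicted by Section 10.4.1, and the word 'latest' in the rule does real work: it picks the last reading of the day, which is the one at 1 hour.

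Readings at 30 minutes and 1 hour are of interest because they can show an acute effect of the first injection. If the last of them is the reference, that effect is absorbed into the Baseline. It leaves the change-from-Baseline and Table 10-6 outputs, and every later change in that subject is shifted by the same amount.

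**Working it through.** The plan gives no figure to reproduce. The check is to apply its written rules to one assumed series.

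**Which reading is the Baseline?**

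1. Candidates on Day 1 (Section 10.4.1): pre-dose, 30 minutes, 1 hour.
2. Are the post-dose readings eligible? Yes under Section 3.3, because they fall on the day of first dose and blood pressure is not exempted.
3. Which one is taken? The latest, so the 1-hour reading.
4. Is anything stated otherwise? Section 10.4.1 describes a display of the readings and their mean and does not assign a Baseline. The default stands.

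**What follows for the outputs?** The readings below are assumptions, not figures from the SAP: systolic 118 pre-dose, 95 at 30 minutes, 88 at 1 hour, and 112 at Week 4. Change = value minus Baseline. The low flag needs a value below 90 and a fall of at least 20.

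| Baseline used | Baseline (mmHg) | 1-hour change | 1-hour reading flagged low? | Week 4 change |
|---|---|---|---|---|
| Pre-dose | 118 | 88 - 118 = -30 | Yes | 112 - 118 = -6 |
| Section 3.3 as written (1 hour) | 88 | 0, as it is the Baseline itself | No | 112 - 88 = +24 |
| Mean of the three | (118 + 95 + 88)/3 = 100.3 | 88 - 100.3 = -12.3 | No | 112 - 100.3 = +11.7 |

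Under the rule as written, no Day 1 reading is post-Baseline, so none can enter the markedly abnormal summary.

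**General form.** Let P be the pre-dose value and P - d the 1-hour value. A later value V has change V - P from pre-dose and V - (P - d) = (V - P) + d from the 1-hour reading. Every later change rises by d: a fall of 5 to 30 mmHg at 1 hour adds 5 to 30 mmHg.

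**Later flags are also affected.** Suppose the Week 4 value were 85 in the same subject. From pre-dose the fall is 118 - 85 = 33, which is flagged. From the 1-hour Baseline it is 88 - 85 = 3, which is not.

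**The case against.** The best reply is that Section 3.3 only makes a post-dose value eligible, and that its context is an assessment recorded out of order, not a planned post-dose timepoint. Other text leans towards a pre-dose Baseline: the sentence that treats Baseline as missing when nothing was measured before dosing, the rule that component scores use measurements recorded before dosing, and the listing of vital signs by time relative to dosing. A sensible programmer might well use the pre-dose reading.

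This shows that the intent may be sound, but it does not change what the rule selects. Eligible combined with latest still picks the 1-hour value. The missing-Baseline sentence applies only when no pre-dose value exists, so it does not choose between pre-dose and post-dose when both are present. The component-score rule does not concern blood pressure.

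Parts of the reply do stand, and they limit the point. A reader might infer that an acute fall would be hidden. It would not: each Day 1 reading is summarized and listed, so the fall stays visible descriptively. Adverse events at first administration are listed (Section 10.2.1), and acute anaphylactic events, by an algorithm that includes hypotension terms, have their own table (Section 10.2.4.7 and Appendix 1). A reader might also extend the point to all vital signs, but only blood pressure has stated post-dose readings on Day 1. Nor does the SAP call the mean of the three readings a Baseline. Finally, an upward shift alone cannot create a markedly high flag, because Table 10-6 also requires a value above 180 systolic or 105 diastolic.

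**Conclusion.** The point holds for blood pressure. The rule as written gives a post-injection reference for changes from Baseline and for Table 10-6, and no other text corrects it. The rule reaches every subject with a 1-hour Day 1 reading, out of about 390 planned. The size of the error in any one subject equals the change between the pre-dose and 1-hour readings. For most subjects that may be small, and the SAP gives no data on it. The numerical example rests on assumed readings and shows the mechanism, not an expected frequency.

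The damage is confined to the blood pressure change and markedly abnormal outputs, including the low and high flags in the listing. Efficacy analyses are not affected. This should be corrected, because it concerns a safety derivation and the remedy is simple.

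**What to change.** Add to Section 3.3 or Section 10.4.1 that Baseline for blood pressure is the last value recorded before the first injection, by assessment time: the Day 1 pre-dose reading, or Screening if that is missing. Add that the 30-minute and 1-hour Day 1 readings are post-Baseline for change from Baseline and for Table 10-6. The mean of the Day 1 readings may stay as a descriptive summary, with a note that it is not the Baseline.

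The cost is two sentences in the SAP and the matching derivation in the analysis dataset. The timepoints are already collected, so no new data are needed.
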